7.0 Confidentiality of data

- 7.1 Describe how data (both paper and electronic) will be stored to safe-guard confidentiality (e.g. in a locked cabinet, password protected computer): All electronic data will be kept on password protected, encrypted devices within the University of Michigan system which meet current security standards. Any paper records utilized during this review will be kept in a locked cabinet within the Pediatric Surgery research space and/or Pl's office.
- **7.2** Specify who will have access to harvested patient data: Access will be given to personnel approved by the IRB.
- 7.3 Clarify long harvested patient data will be stored and how it will be destroyed when no longer needed: We plan to keep this data for future use as this data will contribute to a future project. The data obtained will help to inform future projects and may be included as we further investigate this cohort/disease.

8.0 Consent Process (if applicable):

Written comprehensive consent will be obtained in a face to face manner in the clinic or patient's hospital room at the initial encounter. Ages 0-6 will are requesting a waiver of assent. If the child is 7-9 years of age or older and neurologically intact, informed assent will also be obtained from the child at that time via oral script. and children 10-17 will provide written assent, with children 10-14 assenting on the written assent document and children 15-17 assenting on the consent document, which one parent provides parental permission on.

For patients who are 7 years old or older and without neurological impairment and who have age appropriate neurodevelopment assent will be obtained. For children less than 7 years of age or with neurological impairment, a request for waiver of informed assent is requested, as this would not be feasible. The oral assent will be used and we will ask the child to "teach back" the information to ensure their understanding.

9.0 Risks and Benefits:

9.1 Overall Risks:

Breach of confidentiality: Breach of confidentiality is not expected, though is always a risk despite measures the study team takes to mitigate the risk.

Silver Nitrate:

Very hazardous in case of skin contact (irritant), of ingestion. Hazardous in case of skin contact (permeator), of eye contact (irritant), of inhalation. Slightly hazardous in case of skin contact (corrosive). The amount of tissue damage depends on length of contact. The parents of the children will recieve instructions on administration of the drug and the duration of contact with the skin. Therefore, likelihood of causing further injury will be minimal. Eye contact can result in corneal damage or blindness. Skin contact can produce inflammation and blistering when a prolonged exposure is done. Education will be given to the parents regarding application and therapy. Inhalation of dust will produce irritation to gastro-intestinal or respiratory tract, characterized by burning, sneezing and coughing. Severe over-exposure can produce lung damage, choking, unconsciousness or death. Prolonged exposure mayresult in skin burns and ulcerations. Over-exposure by inhalation may cause respiratory irritation. There is no anticipated exposure of the respiratory system to the silver nitrate as this is being used only on the abdominal portion

of the skin at the gastric tube site.

Kenalog:

Infrequent is a possible mild eye irritant

Rapidly absorbed through skin, repeated exposure may cause skin dryness or cracking. May be harmful if absorbed through skin. The drug used in the concentration for the study has not been shown to be harmful to skin. Education regarding the potential side effects, application and skin care will be given to the parents. May cause damage to organs through prolonged or repeated exposure if swallowed. May cause damage to organs through prolonged or repeated exposure if inhaled. The drug is being used for topical application and will not be near the respiratory tract. Target Organs adrenal glands, bone, muscle, gastrointestinal tract, immune system, eyes, nervous system, skin, female reproductive organs, (embryo/fetus) Signs and Symptoms Chronic: muscle weakness, muscle pain, bone fractures, infection, oedema, headache, difficulty sleeping, vertigo, restlessness, euphoria, mental disturbance, depression, anxiety, mood changes, seizure disorders, nosebleeds, cough, fever, nausea, vomiting, anorexia, gastrointestinal disturbance, sore throat, dry mouth, taste disturbance, speech difficulty, congestion, redness and swelling of eyes, vision changes, facial swelling, skin thinning, acne, redness and swelling of skin, hives, bruising, superficial burning sensation, tingling. Medical conditions aggravated include: Diabetes, Liver disorders, infection, immunodeficiency, hypertension, myasthenia gravis, osteoporosis, peptic ulcer, psychotic disorders, colitis, kidney disorders. These are infrequently seen in children, and mostly seen in adults.

Soapy washcloth: There are no foreseeable risks involved with using soapy washcloth as an arm in this study.

9.2 Benefits:

This study may provide improved knowledge about the best way to treat granulation tissue in the future. In addition, the benefit of treatment of each patient's granulation tissue outweighs the risk of adverse effects of the treatment.

10.0 Statistical Considerations

ANOVA and Chi square tests will be used to evaluate the differences between the three treatment groups. Actual measurements of the granulation site, blinded evaluation of the pictures and analysis of pre and post surveys will be incorporated into the data analysis.

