Principal Investigator: [name]

IRB Project Title: Granulation tissue at G tube site: treatment with Kenalog vs chemical cauterization with Silver Nitrate vs soap washcloth abrasion

Site(s) where study will be performed: C.S. Mott Children's Hospital

Protocol Version 1.0

IRB approval date: 11/12/2021

NCT02519738

PROTOCOL

Principal Investigator: [name]

IRB Project Title: Granulation tissue at G tube site: treatment with Kenalog vs chemical

cauterization with Silver Nitrate vs soap washcloth abrasion Site(s) where study will be performed: C.S. Mott Children's Hospital

Protocol Version 1.0

1.0 Introduction - Background and Rationale: Hypergranulation tissue surrounding gastrostomy tube sites in pediatric patients is a significant problem. This tissue may cause drainage or bleeding that bothers patients and parents. Numerous methods of treatment are used for treatment of hypergranulation tissue, but no data exists to support one method of treatment over another. We plan to perform a prospective randomized trial of three different therapies (silver nitrate cauterization, topical kenalog, and soapcloth abrasion) to identify the best treatment modality. Steroids topically or by intralesional injection has been used to control granulation or hypertrophied scars/keloid. A pertinent reference pertaining to the use of kenalog are as follows:

Lahiri A, Tsiliboti D and Gaze NR.Experience with difficult keloids. British J of Plastic Surgery. 2001; 54(7):633-635

We will follow the patients via office visit at four and eight weeks after initiation of therapy. Measurements of the granulation tissue and photographs will be obtained pre treatment and at each post treatment visit. In addition parents will be asked to fill out a pre and post treatment survey regarding improvement in symptoms. We plan to enroll 120 patients total with the intention of having 40 participants in each group.

- 2.0 Hypothesis/Key Questions: The aim of this study is to prove that kenalog treatments are equal or superior to conventional cauterization with silver nitrate or use of soapcloth abrasion in reducing granulation tissue which forms following insertion of a feeding gastrostomy tube. We will perform measurements, use photographs and survery parents to answer this question.
- **3.0 Objectives**: Evaluate the use of Kenalog vs Silver nitrate cauterization vs soapcloth abrasion around gastrostomy tube sites to reduce the development of granulation tissue.

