We will follow the patients via office visit at four and eight weeks after initiation of therapy. Measurements of the granulation tissue and photographs will be obtained pre treatment and at each post treatment visit. In addition parents will be asked to fill out a pre and post treatment survey regarding improvement in symptoms. We plan to enroll 120 patients total with the intention of having 40 participants in each group.

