4.0 Selection of Patients

- **4.1** *Inclusion Criteria (list):* birth 17 years of age, granulation tissue present around gastrostomy tube site for at least 1 week
- **4.2** Exclusion Criteria (list): allergy to any of the potential medications (silver nitrate or kenalog), Non-english speaking patients will be excluded due to inability to effectively communicate study details, risks and benefits.
- 4.3 Age Range: 0-17 years of age

5.0 Study Methodology:

Prospective, randomized study utilizing children ages birth to 17 years, with granulation tissue present around their gastrostomy tube for at least one week. Patients will be randomized to one of the three treatment groups in equal numbers. Once the inclusion criteria are met, informed consent will be obtained from the parent and randomization will occur. Patients will be randomized to either Kenalog (0.5% ointment three times a day for three weeks) or cauterization with silver nitrate (three times a week for three weeks) or abrasion/washing with a soap washcloth (once daily for three weeks). At the end of the three week period, if granulation tissue is still present, the patients will undergo a rest period of one week, followed by another three week course. These children will be followed at four weeks and eight weeks via clinic visits. At the clinic visits, photographs and measurements will be obtained and parent surveys completed.

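### Section 10.0 makes no stated use of pre-treatment granulation size and leaves open whether follow-up size or change is analysed; ANCOVA on baseline size settles this and usually gains precision, at almost no cost

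*Combined protocol and SAP*

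**What the plan says.** The protocol commits to a baseline size. Sections 1.0 and 3.0 both state: "Measurements of the granulation tissue and photographs will be obtained pre treatment and at each post treatment visit". Section 5.0 gives the timing: "These children will be followed at four weeks and eight weeks via clinic visits". Allocation is equal across three arms, and the target is stated as "We plan to enroll 120 patients total with the intention of having 40 participants in each group".

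Section 10.0 is two sentences long. The first is the whole of the method: "ANOVA and Chi square tests will be used to evaluate the differences between the three treatment groups". The second lists what will be brought into the analysis: "Actual measurements of the granulation site, blinded evaluation of the pictures and analysis of pre and post surveys". The before-and-after comparison is mentioned there for the surveys only. Neither section 10.0 nor any other section names a covariate, the visit at which size is compared, or the form of the size outcome (follow-up value, change or percent change).

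**The concern.** Two things follow from this silence.

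- **An open choice.** ANOVA on follow-up size and ANOVA on change both fit the text. Their estimates of a treatment difference are not the same: they differ by the baseline difference between the arms. Chance imbalance is not bias over repeated randomisations, and the unadjusted standard error allows for it, but it does move the estimate in this one trial. If the form is chosen after the data are seen, the result can shift by the full imbalance.
- **Lost precision.** Baseline size is collected, but no use of it in the size analysis is specified. ANCOVA on baseline is at least as precise as either reading, apart from the small cost of estimating one slope. Section 2.0 aims to show Kenalog equal or superior to two comparators, and a claim of equality depends on narrow intervals. The documents contain no power calculation, so no spare power has been shown.

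**Working it through.** **Inputs from the documents.** Three arms in equal numbers, 40 each (3 × 40 = 120); size measured before treatment and at four and eight weeks. The documents give no alpha, SD, effect size or power, so 120 cannot be re-derived.

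**Assumptions.** Two-sided 5%; equal SDs before and after treatment; complete data; r = 0.3, 0.5, 0.7; a pairwise difference of 0.5 SD for illustration.

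**1. Variance per patient, in units of SD².**

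- Follow-up size: 1
- Change: 2(1 − r)
- ANCOVA: 1 − r²

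| r | Follow-up | Change | ANCOVA | Saving vs follow-up (r²) | Saving vs change, 1 − (1 + r)/2 |
|---|---|---|---|---|---|
| 0.3 | 1 | 1.4 | 0.91 | 9% | 35% |
| 0.5 | 1 | 1.0 | 0.75 | 25% | 25% |
| 0.7 | 1 | 0.6 | 0.51 | 49% | 15% |

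**2. Pairwise power for 0.5 SD.** Non-central t, standard error √(2 × variance/40), 117 residual df for ANOVA and 116 for ANCOVA.

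| r | Follow-up | Change | ANCOVA |
|---|---|---|---|
| 0.3 | 60.2% | 46.6% | 64.2% |
| 0.5 | 60.2% | 60.2% | 72.6% |
| 0.7 | 60.2% | 81.7% | 87.4% |

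**3. Cost of the covariate.** Estimating the slope inflates the ANCOVA variance by about 1 + 1/(120 − 3 − 2) = 1.0087. With this included, ANCOVA power is 63.9%, 72.2% and 87.1%. In the worst case, r = 0, it is 59.8% against 60.2% for follow-up size; change gives 34.8% there. ANCOVA breaks even with follow-up size where 1 − r² = 1/1.0087, at r of about 0.09. It beats change for any r below 2/1.0087 − 1, about 0.98.

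**4. Three-arm F test.** Take the effect that gives 80% power on follow-up size with N = 120 (f = 0.287). At r = 0.3, 0.5, 0.7 change gives 64.8%, 80.0%, 95.7%, and ANCOVA, inflation included, gives 83.5%, 90.2%, 97.9%. The ranking is the same as for pairs.

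**5. Size of chance imbalance.** The SD of a baseline difference between two arms is √(2/40) = 0.224 SD. The probability that a given pair differs by more than 0.3 SD is 2[1 − Φ(0.3/0.224)] = 18%. The probability that at least one of the three pairs does is 37% (simulation, 2 million draws).

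**6. Effect of an imbalance b.** It shifts the follow-up estimate by r·b and the change estimate by −(1 − r)·b. The gap between them is r·b + (1 − r)·b = b, whatever r is. For b = 0.3 SD the shifts are 0.09, 0.15, 0.21 SD and −0.21, −0.15, −0.09 SD. The gap of 0.3 SD is 0.3/0.224 = 1.3 standard errors of the follow-up difference.

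**7. Resolved sites.** If follow-up size is a normal variable clipped so that half the values are zero, the observed correlations fall to 0.26, 0.43 and 0.60. The saving against follow-up size falls to about 7%, 18% and 36%.

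**The case against.** The strongest reply is that this is a matter of efficiency, not error. Unadjusted ANOVA is valid under randomisation, and a two-sentence summary does not rule out covariates or a repeated-measures ANOVA that uses the baseline. That is correct, and it caps the weight of the point; but text that allows several analyses specifies none of them.

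The size of the gain also rests on assumed inputs. At r = 0.1 there is no gain over follow-up size once slope estimation is counted (60.2% either way), and at r = 0.3 it is about 4 points. Treatment aims to clear the tissue, so zeros could exceed half. In the same clipped model the savings at r = 0.3, 0.5, 0.7 are 5%, 14%, 27% with 70% zeros and about 2.5%, 7%, 13% with 90%. With that many zeros, resolved or not resolved may be the more informative outcome. These limits stand, so the 9%, 25% and 49% savings are a no-zeros case.

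The comparison with change is affected as well, because it assumes equal SDs. With half zeros the follow-up SD drops to about 0.58 of baseline and the saving against change rises to roughly two thirds, which strengthens the case for ANCOVA.

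Lastly, the figures are for untransformed size, while a scale that handles zeros is advised. On ranks without zeros the savings are similar (8%, 23%, 47%); power was not worked out for ranks or for log with an offset. None of this reverses the direction.

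**Conclusion.** The concern holds, as an improvement that should be made rather than a flaw that invalidates the trial. That the visit, the outcome form and the use of baseline are unspecified is plain from the text. That the two unadjusted readings differ by the full baseline imbalance does not depend on r.

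The precision gain does depend on r, which the documents do not give. Over r = 0.3 to 0.7 with no zeros, ANCOVA adds about 4 to 27 power points over follow-up size and about 6 to 18 over change, for a 0.5 SD pairwise difference with 40 complete patients per arm. With many zeros or r near 0 the gain over follow-up size becomes small. The most that can be lost is under half a point. Confidence in the size of the gain is moderate; in its direction, high.

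**What to change.** In section 10.0, replace the ANOVA on size with wording such as:

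> Granulation size at the [four- or eight-week; name one] visit will be compared between arms by ANCOVA, with treatment arm as factor and pre-treatment size as covariate, on [one scale that handles zeros: ranks, or log with a stated offset].

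The sponsor should fill in both brackets before outcome data are examined; leaving two scales open would recreate the problem. Log with an offset yields a treatment difference with an interval, which suits the equal-or-superior aim better than ranks alone.

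Where the survey gives a score at both times, analyse the post-treatment score in the same way with the pre-treatment score as covariate. Keep the chi-square test for resolved or not resolved; a baseline-adjusted analysis of resolution can be secondary and optional.

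The cost is two or three sentences and one degree of freedom per model. No extra data, visits or patients are needed.

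### The aim is to find the best of three treatments, but Section 10.0 plans only overall three-group tests, with no pairwise comparisons and no rule for calling an arm best

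*Combined protocol and SAP*

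**What the plan says.** Section 1.0 states the purpose as a randomized comparison of "three different therapies (silver nitrate cauterization, topical kenalog, and soapcloth abrasion) to identify the best treatment modality". Section 2.0 puts the hypothesis differently: that "kenalog treatments are equal or superior to conventional cauterization with silver nitrate or use of soapcloth abrasion". Section 3.0 asks only for an evaluation of the three treatments.

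On size, Section 1.0 (repeated under Section 3.0) says: "We plan to enroll 120 patients total with the intention of having 40 participants in each group". Section 5.0 adds: "Patients will be randomized to one of the three treatment groups in equal numbers". Follow-up is at two visits: "These children will be followed at four weeks and eight weeks via clinic visits".

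Section 10.0 is the whole statistical plan and has two sentences. The first is "ANOVA and Chi square tests will be used to evaluate the differences between the three treatment groups". The second lists the data: "Actual measurements of the granulation site, blinded evaluation of the pictures and analysis of pre and post surveys will be incorporated" into the analysis. The document states no pairwise contrast, post hoc procedure, significance level, multiplicity rule, primary outcome or visit, or criterion for calling an arm best.

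**The concern.** An overall ANOVA or chi-square test across three arms has one null hypothesis: all three are equal. Rejecting it supports a single statement, that at least one arm differs from another. The test also rejects when two arms are equally good and the third is poor. Neither stated aim is answered by it. Naming a best arm needs evidence that first place beats second. The Section 2.0 hypothesis needs Kenalog against silver nitrate and Kenalog against washcloth. The third pair, silver nitrate against washcloth, is implied by no hypothesis, yet it is needed if either of those arms might be called best.

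The step from a significant overall test to a named winner is therefore left open until the data are seen. Section 1.0 says no data favour one treatment over another, so a claim from this trial could shape practice. Section 9.1 lists skin injury among the risks of silver nitrate and foresees none for the washcloth. Wrongly preferring one of two equally effective arms could therefore matter to patients.

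**Working it through.** **The plan's own figure.** 3 × 40 = 120, so the total and the per-arm numbers agree. No significance level, power, effect size, SD or event rate is given, so 40 per arm cannot be derived from anything in the document.

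**Inputs.** From the document: three arms, 1:1:1, 40 per arm, ANOVA and chi-square. Assumed, because the document is silent:
- a significance level of 0.05;
- two arms truly equal and the third worse;
- for ANOVA, SD = 1 and a gap of d SD;
- for chi-square, a yes/no clearance outcome at illustrative rates. The plan defines no such outcome.

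**Two decision rules.**
- Rule A (assumed, not written in the plan): after a significant overall test, name the arm with the best observed result, provided it is the sole top arm.
- Rule B (step-down): the overall test is significant, and the top arm also beats both others at two-sided 0.05.

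**ANOVA.** With means 0, 0 and −d, the noncentrality is λ = n × Σ(μᵢ − μ̄)² = 40 × (2/3)d², with 2 and 117 df.
- d = 0.5: λ = 40 × 0.667 × 0.25 = 6.7, power 62%.
- d = 0.7: λ = 40 × 0.667 × 0.49 = 13.1, power 90%.
- d = 0.8: λ = 40 × 0.667 × 0.64 = 17.1, power 96%.

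In at least 99.9% of the significant trials the top arm is one of the two tied arms. The rate of false sole-best claims under Rule A is therefore almost the same as the power of the overall test.

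**Chi-square.** X² = Σ n(p̂ᵢ − p̄)² / [p̄(1 − p̄)] on 2 df, by simulation. At 70/70/40%, 82% of trials are significant and one tied arm is the sole top arm in 75%. The rest, about 9% of the significant trials, are exact ties for top.

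| Assumed truth, 40 per arm | Overall test significant | Rule A: tied arm named sole best | Rule B |
|---|---|---|---|
| 70/70/40% | 82% | 75% | 4.7% |
| 80/80/50% | 86% | 77% | about 5% |
| 60/60/40% | 46% | 43% | 4.4% |
| One arm 0.5 SD worse | 62% | 62% | 4.7% |
| One arm 0.7 SD worse | 90% | 90% | about 5% |
| One arm 0.8 SD worse | 96% | 96% | about 5% |

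With wider gaps the Rule A range widens too, from 26% at 0.3 SD to 99.7% at 1.0 SD. If all three arms clear at 50%, Rule B names a best arm in 1.5% of trials.

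**Why Rule B holds its level.** If all three arms are equal, the overall test protects at 5%. If exactly two are equal, only one pairwise null is true, and it is tested at 5%. With exactly three groups no other configuration contains a true null, so the step-down is a closed procedure and alpha need not be split.

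**Limit of that guarantee.** It covers one outcome at one visit. Three outcome types at two visits make six possible analyses. Applying Rule B to all six (two arms tied, third 0.7 SD worse) gives at least one false best claim in about 26% of trials if the six are independent, and about 16% if they correlate at 0.7.

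**What Rule B costs.** When one arm truly is best:
- at 80/50/50% it is named in about 70% of trials instead of 85%;
- at 75/60/40% it is named in 28% to 29% instead of 77%.

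**The case against.** A reader might infer that the plan, followed as written, would often crown one of two equally good arms. The document does not support that. Section 10.0 contains no naming rule, so Rule A is an assumption. The percentages also need two arms to be truly tied, and the chi-square rows need an outcome the plan never defines. The investigator could run pairwise tests after the overall test, and the wording of Section 10.0 is loose enough to allow it. This objection stands, which is why the rates are offered as illustrations only. It does not close the gap: nothing says which pairs would be tested, how error would be controlled, or what would count as best.

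Two further points have some force. The word best comes from the background section, whereas the formal hypothesis concerns Kenalog. That hypothesis also needs pairwise comparisons, however, and none is planned. Second, in the tied scenarios the arm named is almost never the inferior one, so as a choice of treatment it does no harm to efficacy. The error lies in claiming that one arm is uniquely best, which matters because the listed risks of the arms differ.

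**Conclusion.** The concern holds as a mismatch between aims and analysis. Sections 1.0 and 2.0 need comparisons between particular arms. Section 10.0 names only overall tests, which cannot supply them, and no rule for a best arm exists. That much can be read from the document and rests on no assumption.

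The size does rest on assumptions: 40 per arm, a 0.05 level, two tied arms, and a winner picked by observed rank after a significant overall test. Under these, a tied arm is named sole best in roughly 43% to 96% of trials in the tabulated scenarios, against about 4% to 5% with the step-down rule. This should be corrected before analysis. It is separate from the question of how to show that Kenalog is equal to another arm, which needs a margin.

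**What to change.** First name one primary outcome and one visit. Then add to Section 10.0, in substance:

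- For the primary outcome and visit, if the three-group test is significant at 0.05, all three pairs of arms are compared, each at two-sided 0.05 and each reported with a 95% confidence interval.
- An arm is called best only if it beats both other arms. Otherwise the report states which arms were separated and makes no claim of a single best arm.
- Other outcomes and the other visit are supportive and carry no claim of a best arm.

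This controls error at about 5% for that single outcome and visit only. Tukey comparisons would also serve and are stricter, with a false-best rate of 1.3% to 2.0% for gaps of 0.3 to 1.0 SD.

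The change needs a few sentences and no new data. The real cost is fewer claims of a best arm, as shown above, so the sample size should be rechecked against the rule. With 40 per arm, a single pairwise comparison at 0.05 has 80% power only for a difference of about (1.96 + 0.84) × √(2/40) = 0.63 SD, and beating both other arms is harder.

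### No primary outcome or primary visit is named among three outcomes at two visits, and only the picture evaluation is described as blinded

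*Combined protocol and SAP*

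**What the plan says.** Section 2.0 sets the aim: "The aim of this study is to prove that kenalog treatments are equal or superior to conventional cauterization with silver nitrate" or washcloth abrasion, "in reducing granulation tissue which forms following insertion of a feeding gastrostomy tube". It then brings in all three data sources together: "We will perform measurements, use photographs and survery parents to answer this question".

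Section 5.0 places follow-up at four and eight weeks: "At the clinic visits, photographs and measurements will be obtained and parent surveys completed". The same section makes a second course depend on a judgement: "At the end of the three week period, if granulation tissue is still present", the child has a week's rest and then another three weeks of treatment.

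Section 10.0 is two sentences long. The first names ANOVA and chi-square for the three-group comparison. The second reads "Actual measurements of the granulation site, blinded evaluation of the pictures and analysis of pre and post surveys will be incorporated into the data analysis".

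No section names a primary outcome, a primary visit, an order of importance, a significance level or a multiplicity rule. Blinding is mentioned once, for the pictures. On silver nitrate, Section 9.1 says "The parents of the children will recieve instructions on administration of the drug and the duration of contact with the skin", and it promises parents similar teaching for Kenalog.

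**The concern.** With three outcomes at two visits and no ranking, six three-group results could each be offered as the answer. A reader of the final report could not tell a planned result from a selected one. That matters because the trial sets out to prove something about Kenalog and, in Section 1.0, to identify the best of three treatments.

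The outcomes also differ in how well they are protected. An ointment, a silver nitrate application and a soapy washcloth cannot be mistaken for one another, and parents are taught to apply the two drugs. The survey is therefore open-label in effect. As written, it has the same standing as the one reading that is described as blinded. Knowledge of the arm can produce a difference that is not there. It can also hide a real one, which bears on the part of the aim that speaks of equality.

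**Working it through.** **Inputs from the documents.** Three outcomes (Sections 2.0 and 10.0); two follow-up visits (Sections 1.0, 3.0 and 5.0); 40 per arm in three arms, 120 in total (Section 1.0). The total is consistent: 3 × 40 = 120. No error rate is stated, so there is none to reproduce.

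**Assumptions.** 5% per three-group test, no true difference, and the correlations shown below.

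**Any significant three-group result, independent tests**, 1 − 0.95^k:
- three outcomes at one visit: 1 − 0.95³ = 14.3%
- two tissue outcomes (measurement, picture) at two visits: 1 − 0.95⁴ = 18.5%
- all six: 1 − 0.95⁶ = 26.5%
- five, if the survey has only one post-treatment reading: 1 − 0.95⁵ = 22.6%

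**Correlated tests, all six.** Simulation with 40 per arm, equal correlation among the six underlying variables and at least 20,000 null trials per setting. Mixed coding means clinic size by ANOVA, with picture clear and survey improved as yes/no variables (60% base rate) by chi-square. The documents do not say how the outcomes will be coded.

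| Correlation | Mixed coding | All continuous |
|---|---|---|
| 0.3 | about 25% | about 24% |
| 0.5 | about 23% | about 21% |
| 0.7 | about 20% | about 17% |
| 0.8 | about 19% | about 15% |
| 0.9 | about 16% | about 11–12% |

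One named test stays at about 5% throughout.

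**Significant with Kenalog looking best.** With three exchangeable arms, Kenalog is best in one third of false positives, so one test gives 0.05/3 = 1.7%. Six independent tests give 1 − (1 − 0.05/3)⁶ = 9.6%. In the same simulation with mixed coding the figure is about 9% at correlation 0.3 and about 6% at 0.9. With all outcomes continuous it falls to about 4% at 0.9.

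**Power of two possible picture-based primaries, 40 per arm, 5% two-sided.**
- Size, three-group ANOVA, one arm shifted by d SD: noncentrality = 40 × (2/3) × d². At d = 0.609 this is 9.9, which gives 80% power on 2 and 117 degrees of freedom. A pairwise t-test (78 degrees of freedom, noncentrality d × √20) needs d = 0.634.
- Present or absent, chi-square, assumed 60% against 80% clear: exact enumeration gives 49.7% pairwise, and also 49.7% for three groups at 60%, 60% and 80%.

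**Timing.** Three weeks of treatment plus one week of rest puts the week-4 visit at about the start of any second course. The week-8 visit comes after that course, so it carries the effect of the three-week judgement.

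**The case against.** The best defence is that the wording already leans toward tissue. The aim is about reducing granulation tissue, and Sections 1.0 and 3.0 introduce the survey as an extra: "In addition parents will be asked to fill out a pre and post treatment survey regarding improvement in symptoms". That lean is real, but it is not a ranking, because Section 2.0 uses all three sources to answer the question. Even without the survey, two tissue outcomes at two visits leave four tests.

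Several objections to the size and the remedy stand:
- A reader might take 26% as the chance of a false claim for Kenalog. It is not: it also counts results where Kenalog looks worst or where only the two comparators differ. The figure that favours Kenalog is about 10% or less.
- A reader might infer that the clinic measurements are unblinded. The documents do not say so; they are silent on whether the measurer knows the arm.
- A reader might want a figure for the bias. Any such figure would rest wholly on assumed sizes, so none is given.
- Present or absent at week 8 is not the evident choice of primary. It has low power, and week 8 is the visit exposed to the retreatment judgement.
- Giving the survey secondary rank is a judgement. Section 1.0 motivates the trial by drainage or bleeding that bothers patients and parents.

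**Conclusion.** The concern holds in a limited form. The plan gives three outcomes at two visits equal standing, with no primary and no multiplicity rule, and describes blinding for only one of them. At an assumed 5% per test, the chance of at least one false-positive three-group result among six is 26% if independent. It is about 25% at correlation 0.3 and 11% to 16% at 0.9, against 5% for one named test. The chance of a false positive with Kenalog looking best is about 10% if independent. It is about 9% at 0.3 and 6% at 0.9 with mixed coding (about 4% at 0.9 if all outcomes are continuous), against 1.7%. These figures depend on the assumed level, correlations and coding. That no primary is named does not.

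Bias from knowledge of the arm is plausible for the parent survey and undetermined for the measurements. It could act in either direction, and its size cannot be estimated from the documents.

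The false-positive figures bear on claims of a difference. A reader might think that naming a primary also secures the equality part of the aim. It does not: equality would be read from a non-significant result, and the documents give no margin.

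**What to change.** In Section 10.0, before any data are seen, name one variable from the planned blinded picture evaluation, at one visit, as the single primary. Identify images by code and hide the arm from the evaluator. The sponsor should choose one of two forms:
- picture-read size by ANOVA: 80% power at about 0.6 SD, but it needs a scale in the frame;
- tissue present or absent by chi-square: simpler to score, but only about 50% power for an assumed 60% against 80%.

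Make the other picture variable, the other visit, the clinic measurements and the parent survey secondary and supportive. Label the survey open-label. Report the number of second courses by arm.

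Keeping all six results co-equal with Bonferroni (0.05/6 = 0.0083 each) would also control the error rate. It would raise the pairwise difference detectable with 80% power from about 0.63 to 0.78 SD (normal approximation), and the survey would keep equal standing.

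**Cost.** A few sentences, coded image files and a short scoring form; no new visits or patients.

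**Downsides.** Photographs show height and symptoms less well, so the other outcomes remain useful support. An image may sometimes reveal the arm, since Section 9.1 lists skin effects of silver nitrate. A week-8 primary stays exposed to the three-week judgement, which blinded reading does not remove. How equality would be shown still has to be settled separately.
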